3.1 General Design

This is a study to test whether densely ionizing, high relative biologic equivalence (RBE) radiation in the form of neutron radiation, can improve the response rate to checkpoint inhibitor immunotherapy in patients with advanced urothelial carcinoma. In this trial, the addition of focal radiation is hypothesized to act as a “vaccine” by releasing tumor neoantigens, with the goal being to augment the immune response. Trial schema is shown below in Figure 1 and study calendar in Table 1. Patients with advanced urothelial carcinoma about to receive checkpoint inhibitor therapy (pembrolizumab), with at least two sites of measurable disease per RECIST 1.1, will undergo neutron radiation to 1-3 sites of disease. At least one site of RECIST 1.1 evaluable disease must remain untreated³¹, as only non-radiated sites will serve as index lesions to assess for response rate per iRECIST criteria.³⁰ Asymptomatic lesions are eligible for radiation as the primary goal of the radiation therapy is to induce an immune response.

[figure not shown]

Figure 2. Clinical trial schema.

Table 1. Study Calendar.

	Pre-treatment⁴	Between Dose 2 and 3 of Immunotherapy⁵	4-Weeks After End of Radiation⁶	16-Weeks After End of Radiation⁷
Informed Consent	X			
Medical History	X		X	X
Physical Exam	X		X	X
ECOG Performance Status	X		X	X
Blood Draw¹	X	X	X	X
Radiation Therapy		X		
Tumor biopsy (optional)²		X		X
CT C/A/P³	X		X	X

¹Blood draw will consist of 9 tubes: 8 yellow top tubes (BD Vacutainer #364606 Acid citrate dextrose additives ACD Solution A) and 1 red top tube (BD Vacutainer #367820 Clot Activator) to collect and store the following: 1) 6 tubes of 0.5 ml serum; 2) 2 tubes of 1.0 ml plasma; 3) 4 tubes of 0.5 ml PBMC; and 4) 6 tubes of 1 ml PMBC.

²Tumor biopsy of a radiated or non-radiated site will be performed for patients who consent.

³CT C/A/P is preferred but MRI or PET/CT also acceptable.

⁴All pre-treatment assessments must be performed within 30 days of protocol enrollment, except CT C/A/P which must be within 45 days of protocol enrollment.

Pembrolizumab is typically given every 3 weeks. Dose 2 must happen between 2.5-5 weeks after dose 1, and dose 3 must happen between 6-9 weeks after dose 1.

⁶Acceptable date range is 3 to 6 weeks after radiation ends.

⁷Acceptable date range is 12 to 24 weeks after radiation ends.

Time points for peripheral blood collection are based on prior studies, including Huang *et al.* and Twyman-Saint Victor *et al.* described above^{9,29}, that show peak changes in peripheral blood immune cell populations around 3-6 weeks post start of therapy for checkpoint inhibitor immunotherapy, and changes after radiation treatment that peak around 2-4 weeks but can persist for months after treatment.

After the study period as outlined above, all patients will be followed at least once every 3 months by the treating oncologist per standard of care. Toxicity, disease response, and survival will be recorded at each clinic visit. Patients are considered off-study once disease progression is detected per iRECIST³⁰. Follow up with radiation oncology is not required but records will be obtained from treating oncologist. All correlative studies will be batched for analysis.

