Phase II Trial of Neutron Radiotherapy with Concurrent Checkpoint Inhibitor Immunotherapy (pembrolizumab) in Patients with Advanced Urothelial Carcinoma

Principal Investigator: [name]
Associate Professor
Department of Radiation Oncology
University of Washington Medical Center
[name]
[name]
[contact]
[contact]
Email: [contact]

Co-Investigators: [name]
[name] PhD
[name]
[name], PhD
[name]
[name]
[name], PhD
[name] [name]
[name]
[name]
[name]

Version: 01/08/2019

Study Summary

Title	Phase II Trial of Neutron Radiotherapy with Concurrent Checkpoint Inhibitor Immunotherapy (pembrolizumab) in Patients with Advanced Urothelial Carcinoma
Short Title	Neutron + Pembrolizumab in Advanced Urothelial Cancers
Protocol Number	CC 9940
Phase	II
Methodology	1 Arm Open-Label
Study Duration	2 yrs
Study Center(s)	University of Washington Medical Center
Objectives	To primary objective is to assess whether neutron radiation (with high relative biological effectiveness relative to standard photon radiation) to a single focus of disease in patients with advanced urothelial carcinoma, can improve the overall response rate to standard of care checkpoint inhibitor immunotherapy (pembrolizumab). The primary endpoint is the overall response rate per iRECIST. Secondary objectives are to evaluate toxicity, immune-related clinical responses and immune pharmacodynamic changes, progression-free survival, and overall survival.
Number of Subjects	20 evaluable subjects
Diagnosis and Main Inclusion Criteria	Patients diagnosed with advanced urothelial carcinoma, about to start checkpoint inhibitor immunotherapy (pembrolizumab) per standard of care, and eligible to undergo radiation to at least one site of disease with at least one additional site of disease that is measurable per RECIST criteria. Patient may receive radiation to asymptomatic sites of disease.
Study Product, Dose, Route, Regimen	All treatments are approved standard of care for patients with advanced urothelial carcinoma, including pembrolizumab and neutron radiation to a metastatic site. Dosing of pembrolizumab will be in accordance with their FDA label. Neutron radiation will be administered at a palliative dose/fractionation regimen to a site of disease that is either symptomatic, likely to become symptomatic, or likely to cause minimal toxicity with radiation treatment.

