Example 5	iUPD	iSD	iSD, iUPD, or NE	iSD, iUPD, iCPD, or NE	iSD, iUPD, iCPD, or NE	iSD
Example 6	iUPD	iCPD	Any	Any	Any	iCPD
Example 7	iUPD	iUPD (no iCPD)	iCPD	Any	Any	iCPD
Example 8	iUPD	NE	NE	NE	NE	iUPD

Eight examples are presented for patients with target disease at baseline, but many more scenarios exist following the same principles. Table assumes a randomised study in which confirmation of complete response or partial response is not required. For patients with non-target disease only at baseline, only iCR or non-complete response or non-progression of disease can be assigned at each timepoint (not shown in the table for ease of presentation). "I" indicates immune responses assigned using iRECIST. iBOR=best overall response. iCR=complete response. iPR=partial response. NE=not evaluable. iUPD=unconfirmed progression. iCPD=confirmed progression. iSD=stable disease. RECIST=Response Evaluation Criteria in Solid Tumours.

Table 3: Scenarios of assignments of best overall response using iRECIST

Secondary Objectives:

- Progression free survival.
- Overall survival.
- Safety and tolerability as evaluated by the incidence, severity, duration, causality, seriousness, and type(s) of adverse events as assessed by CTCAE version 4.0

Exploratory Objectives:

- Changes in peripheral blood immune cell subpopulations measured via multi-parameter flow cytometry:
 - Important T-cell subsets using markers such as: CD3/CD8/CD4/Foxp3/CD45RA/CD45RO/CCR7/CD28/CD27/CD57/CD25/HLA-DR/CTLA4/PD-1
 - NK cells will be assessed using CD16/CD56/CD69.
 - B-cells and dendritic cells will be analyzed using: CD19, CD123, CD11c, CD86, MHC class I and II, CD70, and CD54.
 - MDSC will be assessed using: CD11b, CD 14, CD33.
- Next generation sequencing of the T-cell receptor- β locus in genomic DNA from sorted CD4+ and CD8+ T cell subsets from blood samples using the TRB ImmunoSeq kit (Adaptive Biotechnologies).
- Tumor biopsies (pre- and post-treatment of a non-radiated site) in select patients who consent will be assessed for: cell death, tumor infiltrating lymphocytes, expression of cell surface markers including HLA, PDL1, etc., and undergo multiparameter flow cytometry as well as TCR sequencing.

3 Study Design

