3.3. Eligibility Criteria

A. Inclusion Criteria

- Pathologically proven (either histologic or cytologic) diagnosis of urothelial carcinoma
- At least two sites of disease that are measurable by RECIST 1.1 criteria
- Eligible for checkpoint inhibitor immunotherapy (pembrolizumab) per standard of care
- No history of autoimmune disease requiring systemic therapy (e.g. steroids or biologic agents).
- Adequate organ function
 - Hematologic
 - ANC ≥ 1500 /mCL
 - Platelets $\geq 100,000$ /mCL
 - Hemoglobin > 9 g/dL
 - Renal
 - Creatinine ≤ 1.5 x upper limit of normal (ULN) OR ≥ 60 mL/min
 - Hepatic
 - Total bilirubin ≤ 1.5 ULN OR direct bilirubin \leq ULN if total bilirubin > 1.5 x ULN
 - AST and ALT ≤ 2.5 x ULN OR < 5 x ULN if patient has live metastasis
 - Albumin ≥ 2.5 g/dL
 - Coagulation
 - INR or PT ≤ 1.5 x ULN unless on anticoagulation therapy, in which case PT or PTT should be in the therapeutic range
 - PTT ≤ 1.5 x ULN unless on anticoagulation therapy, in which case PT or PTT should be in the therapeutic range

- Eligible for neutron radiation treatment to 1-3 sites of metastatic disease (lesions do not have to be symptomatic)
- No steroids for at least 2 weeks prior to enrollment, and patient must not be expected to require steroids during the study period
- Zubrod Performance Status 0-2
- Age \geq 18
- Patient must sign study specific informed consent prior to study entry
- Patients who are sexually active must use medically acceptable forms of contraception
- Life expectancy must be $>$ 3 months

B. Exclusion Criteria

- Has a known history of active TB (Bacillus Tuberculosis)
- Hypersensitivity to pembrolizumab or any of its excipients
- Has a known additional malignancy that is progressing or requires active treatment
- Has received prior therapy with an anti-PD-1, anti-PD-L1, or anti-PD-L2 agent.
- Has a known history of Human Immunodeficiency Virus (HIV) (HIV 1/2 antibodies).
- Has known active Hepatitis B (e.g., HBsAg reactive) or Hepatitis C (e.g., HCV RNA [qualitative] is detected).
- Has known psychiatric or substance abuse disorders that would interfere with cooperation with the requirements of the trial
- Has a history or current evidence of any condition, therapy, or laboratory abnormality that might confound the results of the trial, interfere with the subject's participation for the full duration of the trial, or is not in the best interest of the subject to participate, in the opinion of the treating investigator.

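### Sections 2 and 3.1 ask only for evaluable unirradiated disease where the synopsis asks for measurable, so a patient can meet 3.1 and 3.3 yet be unable to score a partial response

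*Combined protocol and SAP*

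**What the plan says.** Four places describe the disease that must be left to assess response.

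- **Study Summary, main inclusion criteria:** the patient can have at least one site irradiated, "with at least one additional site of disease that is measurable per RECIST criteria".
- **Section 2, Primary Objective:** response is read on lesions that were not irradiated and are RECIST *evaluable*.
- **Section 3.1:** patients "with at least two sites of measurable disease per RECIST 1.1, will undergo neutron radiation to 1-3 sites of disease". The next sentence says "At least one site of RECIST 1.1 evaluable disease must remain untreated", "as only non-radiated sites will serve as index lesions to assess for response rate per iRECIST criteria".
- **Section 3.3, inclusion criteria:** "At least two sites of disease that are measurable by RECIST 1.1 criteria" and, as a separate item, "Eligible for neutron radiation treatment to 1-3 sites of metastatic disease". Nothing links the two items.

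Two further statements matter. The note under the iRECIST best-response table in Section 2 (Table 3) says that for patients whose baseline disease is all non-target, "only iCR or non-complete response or non-progression of disease can be assigned at each timepoint". Section 3.2 defines the overall response rate as the percentage of patients with a PR or CR.

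**The concern.** Section 3.1 uses *measurable* and *evaluable* in consecutive sentences, so a site may take them as different standards. The documents do not define *evaluable*. The RECIST table in Section 2 defines measurable lesions by size and classes all other disease as non-target.

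If *evaluable* is read as the looser term, a patient can be treated within the counts in 3.1 and 3.3 and be left with only non-target disease for the primary endpoint. One of the two ways to count as a responder is then closed before treatment starts, for a reason unrelated to the treatment. With 20 patients, even one or two such cases matter.

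**Working it through.** **Step 1. Which patients are affected.** Let M be the number of measurable sites and R the number irradiated. Sections 3.1 and 3.3 give M ≥ 2 and 1 ≤ R ≤ 3. No measurable site is left only if all M are irradiated, which needs M ≤ R. Hence 2 ≤ M ≤ R ≤ 3:

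- R = 1: impossible, because at least one measurable site remains.
- R = 2: M = 2, both irradiated.
- R = 3: M = 2 or 3, all irradiated.

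In each case one further untreated, non-measurable site is needed to meet the *evaluable* condition in 3.1.

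**Step 2. The affected patient against each text** (M = 2, both irradiated, one non-measurable site untreated).

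| Text | Requirement | Met? |
|---|---|---|
| 3.1 | Two measurable sites; 1–3 irradiated; one evaluable site untreated | Yes, if *evaluable* is looser than *measurable* |
| 3.3 | Two measurable sites; eligible for radiation to 1–3 sites | Yes |
| Synopsis | Measurable site additional to the irradiated one | No, on the natural reading |
| Section 2, Table 3 note | Non-target disease only | iCR possible, iPR not |

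**Step 3. The plan's own power figure.** Section 3.2 gives 80% power with N = 20, 20% against 40%, one-sided 0.05, and names no test. By exact binomial, P(X ≥ 7 | 20, 0.2) = 0.0867 and P(X ≥ 8 | 20, 0.2) = 0.0321, so the rule is at least 8 of 20. Power is P(X ≥ 8 | 20, 0.4) = 0.584. The 80% is not reproduced. That is a separate matter and adds no weight here; 58.4% serves only as the baseline for differences.

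**Step 4. Illustration of the cost.** Suppose k of 20 patients have only non-target disease and chance q of iCR, while the others respond at 40%. Then

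power = Σ_y P(Bin(k, q) = y) × P(Bin(20 − k, 0.4) ≥ 8 − y).

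The documents give neither k nor q; both are assumed. For k = 1 and q = 0 this is P(Bin(19, 0.4) ≥ 8) = 0.512.

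| k | Expected rate, q = 0 | Power, q = 0 | Power, q = 10% |
|---|---|---|---|
| 0 | 40% | 58.4% | 58.4% |
| 1 | 38% | 51.2% | 53.0% |
| 2 | 36% | 43.7% | 47.4% |
| 3 | 34% | 36.0% | 41.7% |
| 4 | 32% | 28.4% | 36.0% |

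Each added patient costs between 7.2 and 7.7 points with q = 0, and between 5.4 and 5.7 points with q = 10%.

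**Step 5. Direction.** With q = 0 and a 20% rate in the others, the chance of 8 or more responders falls from 0.0321 (k = 0) to 0.0233 (k = 1) and 0.0163 (k = 2). In this illustration the effect is a lost true finding and not a false positive.

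**The case against.** The case on the other side is substantial.

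- **Intent.** The synopsis points to a measurable unirradiated site. Section 3.1 asks for two measurable sites just before the loose sentence, which suggests one to irradiate and one to measure. This stands as evidence of intent, but the formal eligibility list in 3.3 does not carry it over. Read very literally, even the synopsis's additional site could itself be irradiated. Calling the untreated sites index lesions does not settle it, because Section 5.3 uses that term for the irradiated target.
- **Rarity.** The case needs at least two irradiated sites covering all measurable disease. The synopsis objective speaks of one focus, and Sections 5.5 and 5.6 provide for plan review by the principal investigator and by at least two physicians. This stands: the frequency is probably low. However, 3.1, 3.3 and 5.1 expressly allow up to three sites, and neither review is asked to check for a measurable untreated lesion.
- **Size.** The power loss rests on assumed inputs. The sample is given as 20 evaluable subjects with *evaluable* undefined. If such patients were set aside and replaced, the cost would be extra accrual and power would not fall. This stands, and the table is only an illustration.

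A reader might infer that the protocol flatly allows enrolment without a measurable response lesion, or that such a patient can never count as a responder. The documents support neither. The natural reading of the synopsis excludes the patient, and iCR remains possible.

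**Conclusion.** The point holds as an inconsistency between the synopsis on one side and Sections 2, 3.1 and 3.3 on the other, with a consequence for the primary endpoint. A patient can meet 3.1 and 3.3 and be unable to score iPR, although the natural reading of the synopsis would exclude that patient. The wording conflict is certain. How often it would matter is unknown.

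The cost of about 5 to 8 points of power per patient depends on five assumptions: an exact test with at least 8 of 20, a 40% rate in the other patients, a 0 or 10% chance of iCR in the affected ones, one to four such patients, and no replacement. It should not be read as an estimate of power that the trial has lost. The correction is worth making because it is nearly free and protects a small single-arm endpoint.

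**What to change.** 1. In Section 2 (Primary Objective) and Section 3.1, replace *evaluable* with *measurable* where the unirradiated disease is described.
2. In Section 3.3, add an inclusion criterion: *at least one RECIST 1.1 measurable lesion must remain non-irradiated*. This matches the natural reading of the synopsis.
3. Keep the existing criterion of two measurable sites. It is stricter than the synopsis, which does not ask that the irradiated site be measurable, but relaxing it is a separate eligibility choice and is not needed to close this gap. If the sponsor does change it, 3.1 and 3.3 must change together.

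The cost is a wording amendment with no new procedures and no change to N, the significance level or the analysis. The downside is that a rare patient whose measurable sites would all be irradiated is no longer eligible, or has fewer sites available for irradiation.

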3.2. Statistical Plan

This is a single-arm phase 2 study with the primary endpoint of overall response rate per iRECIST. Overall response rate will be calculated as the percentage of patients achieving a PR or CR, and will be presented along with the 95% CI. Historical data suggest a response rate of 20%, and we hypothesize a true response rate of 40% with the proposed treatment. With 20 patients, we'll have 80% power to observe an estimated response rate that is statistically significantly higher (at the one-sided significance level of .05) than the fixed rate of 20%. Secondary endpoints overall and progression-free survival will be estimated using the method of Kaplan and Meier with 95% CI obtained using Greenwood estimates of variance. Toxicities as assessed by CTCAE version 4.0 will be summarized as the proportion of patients with such toxicities, in addition to total number of toxicities (allowing for multiple toxicities within a patient) among all patients. The exploratory endpoints, change in peripheral blood cell populations will be assessed by estimating the average change between pre- and post-treatment, and these differences will be calculated for each time point; the one-sample t-test will be used to test the null hypothesis that the change is equal to zero. Trends for changes in differences from pre-treatment to post-treatment across time will be assessed using generalized linear models. Similar methods will be used to assess change in tumor biopsies for patients who consent to such analyses, where changes from pre- to post-treatment will be examined for cell death, tumor-infiltrating lymphocytes and expression of various cell-surface markers.

Should this regimen be deemed to be potentially efficacious as defined above, consideration will be given to conduct a subsequent randomized study designed to compare neutron radiation plus checkpoint inhibitors versus checkpoint inhibitors alone.

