Complete response, partial response, or stable disease	Cannot have met criteria for progression before complete response, partial response, or stable disease	Can have had iUPD (one or more instances), but not iCPD, before iCR, iPR, or iSD
Confirmation of complete response or partial response	Only required for non-randomised trials	As per RECIST 1.1
Confirmation of stable disease	Not required	As per RECIST 1.1
New lesions	Result in progression; recorded but not measured	Results in iUPD but iCPD is only assigned on the basis of this category if at next assessment additional new lesions appear or an increase in size of new lesions is seen (≥ 5 mm for sum of new lesion target or any increase in new lesion non-target); the appearance of new lesions when none have previously been recorded, can also confirm iCPD
Independent blinded review and central collection of scans	Recommended in some circumstances—eg, in some trials with progression-based endpoints planned for marketing approval	Collection of scans (but not independent review) recommended for all trials
Confirmation of progression	Not required (unless equivocal)	Required
Consideration of clinical status	Not included in assessment	Clinical stability is considered when deciding whether treatment is continued after iUPD

“i” indicates immune responses assigned using iRECIST. RECIST=Response Evaluation Criteria in Solid Tumours. iUPD=unconfirmed progression. iCPD=confirmed progression. iCR=complete response. iPR=partial response. iSD=stable disease.

Table 1: Comparison of RECIST 1.1 and iRECIST

B	Timepoint response with no previous iUPD in any category	Timepoint response with previous iUPD in any category*
Target lesions: iCR; non-target lesions: iCR; new lesions: no	iCR	iCR
Target lesions: iCR; non-target lesions: non-iCR/non-iUPD; new lesions: no	iPR	iPR
Target lesions: iPR; non-target lesions: non-iCR/non-iUPD; new lesions: no	iPR	iPR
Target lesions: iSD; non-target lesions: non-iCR/non-iUPD; new lesions: no	iSD	iSD
Target lesions: iUPD with no change, or with a decrease from last timepoint; non-target lesions: iUPD with no change, or decrease from last timepoint; new lesions: yes	Not applicable	New lesions confirm iCPD if new lesions were previously identified and they have increased in size (≥5 mm in sum of measures for new lesion target or any increase for new lesion non-target) or number; if no change is seen in new lesions (size or number) from last timepoint, assignment remains iUPD

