Target lesions: iSD, iPR, iCR; non-target lesions: iUPD; new lesions: no	iUPD	Remains iUPD unless iCPD is confirmed on the basis of a further increase in the size of non-target disease (does not need to meet RECIST 1.1 criteria for unequivocal progression)
Target lesions: iUPD; non-target lesions: non-iCR/non-iUPD, or iCR; new lesions: no	iUPD	Remains iUPD unless iCPD is confirmed on the basis of a further increase in sum of measures ≥5 mm; otherwise, assignment remains iUPD
Target lesions: iUPD; non-target lesions: iUPD; new lesions: no	iUPD	Remains iUPD unless iCPD is confirmed based on a further increase in previously identified target lesion iUPD in sum of measures ≥5 mm or non-target lesion iUPD (previous assessment need not have shown unequivocal progression)
Target lesions: iUPD; non-target lesions: iUPD; new lesions: yes	iUPD	Remains iUPD unless iCPD is confirmed on the basis of a further increase in previously identified target lesion iUPD sum of measures ≥5 mm, previously identified non-target lesion iUPD (does not need to be unequivocal), or an increase in the size or number of new lesions previously identified
Target lesions: non-iUPD or progression; non-target lesions: non-iUPD or progression; new lesions: yes	iUPD	Remains iUPD unless iCPD is confirmed on the basis of an increase in the size or number of new lesions previously identified

Target lesions, non-target lesions, and new lesions defined according to RECIST 1.1 principles; if no pseudoprogression occurs, RECIST 1.1 and iRECIST categories for complete response, partial response, and stable disease would be the same. *Previously identified in assessment immediately before this timepoint. "I" indicates immune responses assigned using iRECIST. iCR=complete response. iPR=partial response. iSD=stable disease. iUPD=unconfirmed progression. non-iCR/non-iUPD=criteria for neither CR nor PD have been met. iCPD=confirmed progression. RECIST=Response Evaluation Criteria in Solid Tumours.

Table 2: Assignment of timepoint response using iRECIST

C	Timepoint response 1	Timepoint response 2	Timepoint response 3	Timepoint response 4	Timepoint response 5	iBOR
Example 1	iCR	iCR, iPR, iUPD, or NE	iCR, iPR, iUPD, or NE	iUPD	iCPD	iCR
Example 2	iUPD	iPR, iSD, or NE	iCR	iCR, iUPD, or NE	iCR, iPR, iSD, iUPD, iCPD, or NE	iCR
Example 3	iUPD	iPR	iPR, iSD, iUPD, or NE	iPR, iSD, iUPD, NE, or iCPD	iPR, iSD, iUPD, NE, or iCPD	iPR
Example 4	iUPD	iSD or NE	iPR	iPR, iSD, iUPD, or NE	iPR, iSD, iUPD, iCPD, or NE	iPR

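### With only two post-baseline calendar scans and no confirmation rule written into section 3.2, is the primary response rate left undefined?

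*Combined protocol and SAP*

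**What the plan says.** Section 3.2 opens with the design and endpoint: "This is a single-arm phase 2 study with the primary endpoint of overall response rate per iRECIST". It then gives the estimator: "Overall response rate will be calculated as the percentage of patients achieving a PR or CR", with a 95% confidence interval. It does not mention confirmation, a closing date for assessments, or the class of a response that is never re-assessed.

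The confirmation rule is in the iRECIST material reproduced in section 2. (The comparison table there and the study calendar in section 3.1 are both numbered Table 1; they are named by content here.) On confirmation of complete or partial response, the RECIST 1.1 column of the comparison table reads "Only required for non-randomised trials", and the iRECIST column adopts the same rule. On response after unconfirmed progression (iUPD), it says "Can have had iUPD (one or more instances), but not iCPD, before iCR, iPR, or iSD". The best-overall-response examples carry the note "Table assumes a randomised study in which confirmation of complete response or partial response is not required", so they do not describe this design.

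The study calendar in section 3.1 has a baseline scan and two later ones, 3 to 6 and 12 to 24 weeks after radiation ends. Section 3.1 then continues: "After the study period as outlined above, all patients will be followed at least once every 3 months by the treating oncologist". It adds that disease response is recorded at each of those visits, and that a patient leaves the study when progression under iRECIST is found.

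**The concern.** Confirmation takes two assessments that both show response. If only the calendar scans counted, a confirmed responder would have to be in response at the first of them, which can fall early in pembrolizumab treatment. A patient with iUPD at the first scan and partial response at the second follows a path that iRECIST expressly allows, yet would have no calendar scan left to confirm it. The footnote to the timepoint-response table says that "if no pseudoprogression occurs, RECIST 1.1 and iRECIST categories for complete response, partial response, and stable disease would be the same". A calendar-only count would therefore add no responders beyond confirmed RECIST 1.1, and the choice of iRECIST would do nothing for the primary endpoint.

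If follow-up assessments do count, section 3.2 gives no date at which counting stops, so the result could depend on when the data are cut. With 20 patients, one or two responders can decide whether the rate is declared above 20%. A loose responder definition for the primary endpoint therefore deserves a check.

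**Working it through.** **The plan's own figure.** Section 3.2 states 80% power for n = 20, 20% versus 40%, one-sided 0.05. By the exact binomial, 8 or more of 20 has P(X ≥ 8 | 0.20) = 0.0321 and P(X ≥ 8 | 0.40) = 0.584; 7 or more of 20 gives 0.0867 and 0.750. The 80% is not reproduced. That is a separate matter and does not bear on how responses are confirmed.

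**Timing.** Inputs are the calendar windows and the dose windows in section 3.1: "Dose 2 must happen between 2.5-5 weeks after dose 1, and dose 3 must happen between 6-9 weeks after dose 1". Radiation lies between doses 2 and 3.

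- Gap between the two calendar scans: 12 − 6 = 6 weeks at least, 24 − 3 = 21 weeks at most, 16 − 4 = 12 weeks nominal.
- First scan, counted from dose 1: 2.5 + 3 = 5.5 weeks to 9 + 6 = 15 weeks, taking radiation to end by dose 3.
- Second scan, counted from dose 1: 2.5 + 12 = 14.5 weeks to 9 + 24 = 33 weeks.
- First follow-up visit, taking 3 months as 13 weeks: at latest 24 + 13 = 37 weeks after radiation.

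**Which responses can be confirmed, and where.**

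| First scan | Second scan | Calendar scans only | Follow-up assessments included |
|---|---|---|---|
| response | response | confirmed | confirmed |
| stable | response | not confirmable | confirmed if still in response later |
| iUPD | response | not confirmable | confirmed if still in response later |

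The counts differ only for responses first seen at the second scan.

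**Which count the text supports.** There are three candidates.

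1. *Any partial or complete response, confirmed or not.* Section 3.2 read in isolation would allow it. But the endpoint is defined by iRECIST, and the comparison table requires confirmation in a non-randomised trial. This count is ruled out.
2. *Confirmed response on calendar scans only.* Nothing in section 3.2 imposes this limit. Section 3.1 has disease response recorded at every later visit and ends study participation only at iRECIST progression, which the comparison table says must itself be confirmed. A patient with iUPD, or in response at the second scan, is therefore still on study.
3. *Confirmed response on all recorded assessments until progression.* This uses the rule in section 2 and the data collected under section 3.1. Section 6.1 also supports it: pembrolizumab stops for progression only when that progression is confirmed radiographically, which presupposes imaging beyond the calendar in patients still on treatment. So does the secondary endpoint of progression-free survival.

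The third count is the one an analyst would reach.

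**What the second count would cost, for scale.** Suppose the true confirmed rate is 40% and a share L of responders, first seen at the second scan, is dropped. Then p = 0.40 × (1 − L) and the expected number counted is 20p. The documents give no value for L, so those below are assumptions. Section 3.2 names no test, so two cut-offs are shown: 8/20 from the exact test, and 7/20 from an uncorrected z-test, where z = (0.35 − 0.20)/√(0.20 × 0.80/20) = 1.677, above 1.645.

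| L | p | Expected responders | P(X ≥ 8) | P(X ≥ 7) |
|---|---|---|---|---|
| 0 | 0.40 | 8.0 | 0.584 | 0.750 |
| 0.10 | 0.36 | 7.2 | 0.436 | 0.620 |
| 0.25 | 0.30 | 6.0 | 0.228 | 0.392 |
| 0.50 | 0.20 | 4.0 | 0.032 | 0.087 |

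These losses would matter, but they arise only under a reading the plan does not support and with shares it does not give. They are not a property of the plan.

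**The case for a change.** The strongest contrary case is that iRECIST settles the need for confirmation but not the data to which it applies. Section 3.1 places the quarterly visits after the study period, ties them to standard care and sets no scan dates. A recorded disease response at a clinic visit is not necessarily a scan. Two careful analysts could choose different closing dates and count different responders. The trial is open-label, so the investigators see responses as they occur. A few sentences would settle this at no cost, and the plan also does not say whether the 20% benchmark is a confirmed rate.

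Part of this stands. No closing date, minimum confirming interval or follow-up imaging schedule is stated, and the basis of the benchmark is not given. A response first seen at the second scan and never imaged again would remain unconfirmed.

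Each of these has an ordinary answer within the plan. An unconfirmed response is not a response when confirmation is required, so its class follows from the rule. A short minimum interval would change nothing for the calendar pair, which are always at least 6 weeks apart. Later data can add a confirmed response but cannot remove one already established, so the closing date affects how complete the count is and not whether it is valid. The Study Summary gives a study duration of two years, and the interim contents listed in section 8.2 do not include response, so the plan does not provide for repeated looks at the rate. Any particular interval or date written in now would be a choice among reasonable options, not the correction of an error.

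**Conclusion.** No change follows. The observation is accurate: section 3.2 is terse, and the two calendar scans cannot by themselves confirm a response first seen at the second. The step from there to a defective primary endpoint does not hold. Sections 2, 3.1 and 6.1 together lead to confirmed iRECIST response on non-irradiated lesions, using every assessment recorded until progression, and that is a sound response rate.

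What remains is a gap in detail, confined to patients who first respond 12 to 24 weeks after radiation. For them the next follow-up visit falls at latest about 37 weeks after radiation. The number of such patients cannot be worked out from the documents, so no effect on power or on the estimate can be attributed to the plan.

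The conclusion rests on two assumptions: that progression under iRECIST in section 3.1 means confirmed progression, as the comparison table says, and that patients continuing pembrolizumab are imaged in routine care, as the stopping criterion in section 6.1 implies.
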